## 6.2.11. Bioanalytical and Pharmacokinetic/Pharmacodynamic Methods

Pharmacokinetic (PK) analyses will be performed according to a separate PK analysis plan.

## 6.2.12. Rb Expression Analyses

Rb protein which governs cell-cycle progression in mid-G1 is a major target of CDK4 and CDK6. Cancer cells must express wild-type Rb in order for a CDK4/6 inhibitor to be able to dephosphorylate Rb and thereby cause cell-cycle arrest. Therefore, it is hypothesized that tumors lacking in Rb expression are less likely to respond to abemaciclib relative to the response that is seen in tumors that do express Rb. In the comparator arm, Rb expression is not expected to affect the observed clinical response.

In this study, Rb expression in the nucleus of target cells obtained from formalin-fixed, paraffin embedded tumor tissue was assessed using an immunohistochemistry assay (IHC). The assay as validated is scored qualitatively, with "Positive" expression defined as a tumor showing minimal (1+) specific staining for Rb in at least 10% of target cells and "Negative" expression defined as less than 10% of cells with specific staining, or no specific staining present.

All patients for whom valid IHC results are available at the time of study database lock (hereafter referred to as the Rb population) will be analyzed in the following ways:

- Rb protein expression status will be summarized for all patients in the Rb population by treatment arm as well as overall.
- The patient and disease characteristics obtained at the baseline visit will be summarized and compared between the Rb population and the ITT population.
- Assess if the dichotomized (Positive/Negative) Rb protein expression status observed in tumor tissue is predictive of Abemaciclib treatment benefit with respect to OS, PFS and ORR.

## 6.2.13. Health Outcomes and Quality of Life Evaluations

Patient-reported outcomes are measured through paper versions of the following:

- MD Anderson Symptom Inventory- Lung Cancer (with 11 exploratory items for brain metastases (9) and potential toxicities (2))
- EuroQol 5-Dimension 5 Level (EQ-5D 5L)

Data from the MDASI-LC instrument will be scored as described by Mendoza and colleagues (Mendoza et al. 2011).

Descriptive statistics will be used to describe several subscales and individual items by treatment arm and cycle: symptom severity (13 core items plus lung-cancer items), core severity (13 core items only), interference (6 interference items), 6 individual brain symptom items: irritability (affective); understanding, speaking, concentrating (cognitive); seizures (focal neurologic); appearance (generalized/ disease status) as well as 3 individual items headache, diarrhea and rash.

For each instrument, the analysis will include all cycles for which instrument is planned to measure and at least 25% of patients in each arm have an assessment. If the above criteria are met, a mixed model will be applied to compare treatment arms for symptom severity, core severity, interference subscales, each of 6 individual brain symptom items (irritability, understanding, speaking, concentrating, seizures, and appearance) as well as 3 individual items: headache, diarrhea and rash. The model will include baseline score as a covariate and an unstructured covariance matrix will be utilized if it converges. If the model cannot converge with an unstructured covariance matrix, the covariance matrix will be determined based on the Akaike Information Criterion (AIC).

If a patient does not complete all items on the MDASI-LC, the mean score for a subscale will be calculated when at least 50% of the items for that subscale were answered).

Based on literature (Farrar et al. 2001), it is suggested that worsening of pain by 2 points may be clinically relevant. Time to worsening in pain (worsening by 2 or more points in MDASI pain item or in WHO ladder code based on Table JPBK.6.5 whichever occurs first) will be described using the method of Kaplan and Meier and will be compared between 2 arms by a log-rank test. Worsening-free pain rate at 3, 6, 9, and 12 months (if available) will be compared between treatment arms.

Code	Description
0	No analgesia
1	Aspirin (for pain, not cardiovascular prophylaxis), acetaminophen, nonsteroidal anti-inflammatory drugs
2	Codeine, hydrocodone, pentazocine, oxycodone
3	Oral morphine, hydromorphone, methadone, transdermal fentanyl
4	Parenteral opiates
5	Neurosurgical procedures (blocks)

Table JPBK.6.5.World Health Organization Pain Scale

The EQ-5D 5L data will be scored as described in literature (van Hout et al. 2012). The index score is calculated from a set of item weights to derive a score of 0 to 1, with 1 representing the best health status. United Kingdom (UK) weights will be applied for the base case.

The EQ-5D 5L responses for each item will be summarized by frequency and corresponding percentages by treatment arm and best response category. Descriptive statistics for the index and VAS will be calculated by arm and best response category. Index score and VAS, will be

compared using mixed models. The model will include baseline score as a covariate and an unstructured covariance matrix will be utilized. The analysis will include all cycles for which at least 25% of patients in each arm have an assessment.

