#### 10.2.1.1. MDASI-LC

The MDASI-LC (Mendoza et al. 2011) is a 22-item instrument that includes 13 core symptoms, 6 core interference items, and 3 lung-specific symptoms (coughing, constipation, and sore throat). An additional MDASI page will include 11 exploratory items that are not a standard part of the MDASI-LC instrument. Advanced lung cancer is a leading source of brain metastases, and symptoms related to brain metastases are described by 8 of these exploratory items (weakness on 1 side of body, difficulty understanding, difficulty speaking, seizures, difficulty concentrating, vision, change in appearance, and irritability). These 8 exploratory items for this study are also included as brain-specific items in the MDASI-Brain Tumor instrument. The remaining 3 exploratory items address an additional brain symptom (headache) and expected treatment-related toxicities (diarrhea, rash, or skin change).

"Worst pain" is the first MDASI-LC item, and use of pain medication will be assessed in conjunction with the MDASI-LC assessment as described in Section 10.2.2.

Responses for the MDASI-LC items are captured through the use of 11-point numeric rating scales anchored at 0 (*not present* or *does not interfere*) and ranged through 10 (*as bad as you can imagine* or *completely interferes*). The MDASI-LC recall period is 24 hours, and typical completion time for this instrument is less than 5 minutes.

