#### 12.2.11.1. MDASI-LC

The MDASI-LC population will include all patients who completed at least 1 baseline followed by at least 1 MDASI-LC assessment after 1 cycle of study drug (Cycle 2 Day 1 or later).

The MDASI-LC will be summarized for each assessment period and scored as described (Mendoza et al. 2011). The instrument will be reported as core symptoms (Items 1-13), interference items (Items 14-19) and lung symptoms (Items 14-16), and the 11 additional items will be reported as brain tumor symptoms (Items 23 through 30) and additional 3 items (31-33), as well as each individual item.

For each patient with data from baseline and at least 1 other visit, the maximum change from baseline score will be calculated and summarized for MDASI-LC composite scores, and "worst pain".

Further analysis details will be described in the SAP.

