# 5.2. Secondary Objectives

The secondary objectives of the study are to compare Abemaciclib plus BSC versus erlotinib plus BSC with respect to:

- Progression-free survival (PFS)
- overall response rate (complete response [CR] + partial response [PR]).
- changes in patient-reported pain and disease-related symptoms collected via the MD Anderson Symptom Inventory (MDASI-LC) and changes in health status via European Quality of Life – 5 Dimensions – 5 Level (EQ-5D-5L).
- safety and tolerability
- resource utilization (for example, analgesic type, hospitalization, transfusion)
- pharmacokinetic (PK) and pharmacodynamic (PD) properties of Abemaciclib

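### SAP 6.2.13 lists no MDASI-LC lung-symptom score and none of the three lung items, although protocol 12.2.11.1 says both will be reported; a modest lung-only difference between arms is likely to be missed

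*SAP*

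**What the plan says.** Protocol 10.2.1.1 describes the MDASI-LC as a "22-item instrument that includes 13 core symptoms, 6 core interference items, and 3 lung-specific symptoms (coughing, constipation, and sore throat". An extra page carries 11 exploratory items on brain symptoms and expected toxicities, which the protocol says lie outside the standard instrument.

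Protocol 12.2.11.1 sets out the reporting: "The instrument will be reported as core symptoms (Items 1-13), interference items (Items 14-19) and lung symptoms". It then lists the additional items and ends with "as well as each individual item".

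SAP 5.2 keeps the secondary objective of comparing the arms on "changes in patient-reported pain and disease-related symptoms collected via the MD Anderson Symptom Inventory (MDASI-LC".

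SAP 6.2.13 gives two lists, one for descriptive statistics by arm and cycle and one for mixed models. Both hold the same scores:

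- three subscales: "symptom severity (13 core items plus lung-cancer items), core severity (13 core items only), interference (6 interference items"
- six individual brain items
- headache, diarrhea and rash

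A subscale score is a mean, calculated when at least half of its items are answered. Pain has its own time-to-worsening analysis. No lung-symptom score and no single lung item is in either list.

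**The concern.** The protocol and the SAP differ on which MDASI-LC results will be produced, and the difference falls on the lung module of a lung-cancer instrument in a lung-cancer trial. SAP 6.2.1 allows minor modifications if they are described and justified in the SAP. Section 6.2.13 gives no reason for this one, and the revision history in SAP section 3 does not mention it. Meanwhile nine items from outside the standard instrument receive their own between-arm models.

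If the SAP lists are followed as written, the secondary objective on disease-related symptoms has no between-arm estimate for the lung module. A treatment effect on coughing, for instance, would contribute only as one of 16 items in the severity mean.

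**Working it through.** **Inputs from the documents.** There are 13 core, 6 interference and 3 lung items, each scored on an 11-point scale starting at 0 (protocol 10.2.1.1). Subscale scores are means, and severity is core plus lung items (SAP 6.2.13). Tests are two-sided at 0.05 (SAP 6.2.1). Planned numbers are 270 and 180 patients (SAP 6.1).

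**Assumed, because the documents do not give them.** All items share a common SD *s* and a common inter-item correlation *r*. *r* is varied from 0 to 0.7.

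**Step 1: item count.** 13 + 6 + 3 = 22, which reproduces the protocol's figure. The severity score has 13 + 3 = 16 items, and the lung items carry 3/16 = 18.75% of it.

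**Step 2: raw dilution.** If the arms differ by *d* on each lung item and on nothing else, the lung mean differs by *d* and the severity mean by 3*d*/16.

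- *d* = 1 gives 0.19 in the severity mean.
- *d* = 2 gives 0.375.
- A 1-point shift in the severity mean needs 16/3 = 5.33 points on every lung item.
- A 2-point difference on cough alone gives 2/16 = 0.125 in the severity mean and 2/3 = 0.67 in a 3-item lung score.

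**Step 3: standardised dilution.** The 16-item mean also has a smaller SD than the 3-item mean, so Step 2 alone overstates the loss. The mean of *k* items has SD *s*·√[(1 + (*k*−1)*r*)/*k*]. The standardised effect in the severity mean, relative to that in the lung mean, is therefore

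(3/16) × √[(1 + 2*r*)/3] / √[(1 + 15*r*)/16].

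*s* and the sample size cancel. At *r* = 0 this is 0.1875 × 0.577/0.250 = 0.43; at *r* = 0.3 it is 0.1875 × 0.730/0.586 = 0.23.

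| *r* | 0 | 0.2 | 0.3 | 0.5 | 0.7 |
|---|---|---|---|---|---|
| Relative effect | 43% | 26% | 23% | 21% | 20% |

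**Step 4: illustrative power.** Two-sample normal approximation at one time point, assumed item SD 2.5, all 180 and 270 patients assessed. Each cell shows lung score, then severity mean.

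| *r* | *d* = 0.5 | *d* = 1 |
|---|---|---|
| 0 | 95%, 34% | about 100%, 88% |
| 0.3 | 81%, 10% | about 100%, 26% |
| 0.5 | 72%, 8% | about 100%, 19% |

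With half the patients assessed (90 and 135), the *d* = 1 figures are about 100% and 60% at *r* = 0, and 98% and 15% at *r* = 0.3.

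**Step 5: recovering the lung score.** Severity and core severity are both reported. With complete items, lung mean = (16 × severity − 13 × core)/3. The identity fails when items are missing under the 50% rule, and the SAP plans neither this step nor an interval for it.

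**The case against.** The strongest reply is that nothing has been withdrawn. Protocol 12.2.11.1 still commits to lung symptoms and to every item, and the SAP presents its list as several scores without calling it exhaustive. That is fair as far as it goes. A reader might infer that no lung results will ever exist, and the documents do not show that. They show two lists that specify the outputs, omit these results and give no reason, so the SAP needs to be aligned with the protocol.

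A second reply is that the protocol promises reporting of the lung score, not a test, so the power contrast does not measure a loss against a planned analysis. This stands. The case for a between-arm lung estimate rests on the secondary objective, which is to compare the arms, and not on 12.2.11.1.

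A reader might also infer that a lung-only difference would be almost invisible, or would be reported as no difference. The documents do not support that. They give no SD, correlation or completion rate. With uncorrelated items, SD 2.5 and full data, the severity mean still has 88% power for a 1-point difference. The gap between the severity and core scores would also hint at a lung effect. The SAP's repeated-measures model is not the single-time comparison used above, and no document calls 1 point relevant; the only threshold given is 2 points, for pain. The scenario is narrow as well, since it needs equal effects on all three lung items and none on the 13 core symptoms.

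Lastly, both documents defer to a published scoring paper that was not available for this check. Whatever it defines, only the protocol names a lung score among the outputs.

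**Conclusion.** The concern holds as a discrepancy between protocol and SAP with a real but bounded cost. The omission and the 3/16 weight follow directly from the text. The loss of standardised effect, to roughly 20–43% of what a separate lung score would show, depends only on an assumed common item SD and an assumed correlation between 0.7 and 0. The powers in Step 4 also need an SD and a completion rate, so they are illustrations only. A modest lung-specific difference is likely to be missed under the SAP lists, but not certain to be. Overall survival, PFS and safety are untouched. This is a correction the SAP should make, not a threat to the trial's main conclusion.

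**What to change.** In SAP 6.2.13:

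- Add the 3-item lung-symptom score to the by-arm-and-cycle descriptive list, under the same 50% completeness rule.
- Add coughing, constipation and sore throat to that list as individual items. Reporting them singly matters because constipation sits in the lung score while diarrhea is a frequent abemaciclib event (protocol sections 5 and 9.4.1), so a bowel effect could offset or mimic a cough effect.
- Add the lung score and cough to the mixed-model list, labelled nominal, so that the objective on disease-related symptoms has a lung-module estimate with a confidence interval.
- If the sponsor prefers the present lists, state and justify the departure from the protocol.

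At the same time, reconcile the numbering in protocol 12.2.11.1, which gives "interference items (Items 14-19) and lung symptoms (Items 14-16". The two ranges overlap, and they must be matched to the questionnaire in use before the lung score is programmed.

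The cost is SAP wording and a few more outputs from data already collected. The downside is a small number of extra nominal secondary comparisons.

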#### 6.2.13.1. Resource Utilization

Utilization data will be summarized by category across arms. The following resource utilizations will be described:

- Analgesics (on study treatment and during short term follow up)
- Transfusions (on study treatment and during short term follow up)
- Growth factors (on-study treatment and during short term follow-up)
- Surgery (on study treatment and during short term follow up)
- Hospitalizations (on study treatment and during short term follow up)
- Post discontinuation radiotherapy and systemic therapy.

For categorical variables, frequency and the corresponding proportions will be calculated. Continuous variables will be described by the mean, median, and standard deviation.

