### 5.5. Rationale for Amendment (e)

Due to recent changes in the FDA ertlotinib label and National Comprehensive Cancer Network (NCCN) Guidelines, the Sponsor amended the protocol to address the impact on study enrollment completion, and the need for a larger improvement in OS than that historically targeted for NSCLC patients. In addition, OS is considered the preferred primary endpoint for regulatory approval and hence PFS is removed from the primary objective so all statistical power can be reallocated to enhance the success for OS. The amendment updates include the followings:

- PFS is removed as a co-primary endpoint and changed to a secondary endpoint. With this change OS becomes the sole primary endpoint.
- The final OS analysis will occur when approximately 304 OS events have been observed, a reduction from the current protocol requirement of 407 OS events. With this change, the study will provide 80% statistical power for a new targeted hazard ratio of 0.72.
- Due to the reduced number of targeted OS events, a smaller sample size of approximately 450 patients will be sufficient to reach the 304 OS events for the final analysis (note that current protocol requires 550 patients).

While amending the protocol, the Lilly study team remains blinded to aggregate data and will not be unblinded until the final OS analysis per Section 9.5.

Previously, erlotinib was indicated for the treatment of patients with locally advanced or metastatic NSCLC after failure of at least 1 prior chemotherapy regimen (Tarceva® United States [US] package insert [USPI], 2010) based upon the BR-21 study. In addition, NCCN Guidelines (April 2015) supported erlotinib use as an option for subsequent second line or third line treatment in NSCLC patients (all histologies) for PS 0-3.

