#### Figure JPBK.8.1. Illustration of study design.

Terms used to describe the periods during the study are defined below:

- **Pre-screening:** begins when the pre-screening informed consent form (ICF) is signed for evaluation of FFPE tissue by Study JPBK central laboratory and ends once the *KRAS* mutation status of the tissue is determined (or at discontinuation, if the study ICF is not signed). Pre-screening for *KRAS* mutation status determination is optional. If pre-screening did not occur, determination of *KRAS* mutation status will occur at baseline.
- **Baseline:** begins when the study ICF is signed and ends at the first study treatment (or at discontinuation, if no treatment is given).
- **Study Period:** begins at the first study treatment and ends at study completion. The study period does not include the extension period.
  - **Study Treatment Period:** begins at the first study treatment and ends when the patient and the investigator agree that the patient will no longer continue study treatment. The date of this agreement is to be reported on the case report form (CRF) as the Date of Discontinuation from study treatment.
  - **Postdiscontinuation Follow-Up:** begins the day after the patient and the investigator agree that the patient will no longer continue study treatment. All

randomized patients must be followed during postdiscontinuation regardless of whether study treatment was received.

*Short-term follow-up* begins the day after the patient and the investigator agree that the patient will no longer continue study treatment and lasts approximately 30 days.

*Long-term follow-up* begins the day after short-term follow-up is completed and continues until the patient's death or overall study completion. During long-term follow-up, patients will have a follow-up visit every 60 days ( $\pm 14$  days).

- **Extension Period:** begins after study completion and ends at the end of trial. During the extension period, patients on study therapy who continue to experience clinical benefit may continue to receive study therapy until one of the criteria for discontinuation is met. The extension period includes extension period follow-up.
  - Extension period follow-up: begins 1 day after the patient and the investigator agree that the patient will no longer continue treatment in the extension period and lasts approximately 30 days.

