# 12.2. Statistical and Analytical Plans

# 12.2.1. General Considerations

Statistical analysis of this study will be the responsibility of Lilly.

Efficacy analyses will be based on the intention-to-treat (ITT) analysis set. This population is defined as all patients randomized to study treatment. Patients will be grouped according to randomized treatment.

Safety analyses will be based on the Safety Population, defined as all enrolled patients receiving at least 1 dose of any study drug. Patients will be grouped according to treatment received in Cycle 1.

Pharmacodynamic and/or tailoring biomarker analyses will be based on the subset of patients from the above populations from whom a valid assay result (according to laboratory guideline) has been obtained.

All tests of treatment effects will be conducted at a 2-sided alpha level of 0.05, unless otherwise stated. All confidence intervals (CIs) will be given at a 2-sided 95% level, unless otherwise stated.

Any change to the data analysis methods described in the protocol will require an amendment ONLY if it changes a principal feature of the protocol.

Before unblinding of the aggregate database, minor modifications or clarifications to the data analysis methods may be described and justified in the SAP. The assumptions for each statistical method will be evaluated. If there is violation of assumptions, alternative statistical methods

may be used. Any other change to the data analysis methods described in the protocol, and the justification for making the change, will be described in the CSR.

Additional exploratory analyses of the data will be conducted as deemed appropriate.

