## 6.2.2. Populations

The entered population includes all patients who sign the informed consent document.

The **enrolled or intent-to-treat (ITT)** population includes all randomized patients. The ITT analysis of efficacy data will consider allocation of patients to treatment groups as randomized and not by actual treatment received. This population will be used for all baseline, efficacy, and health economics analyses.

**Safety population** will include all randomized patients who received any quantity of study treatment, regardless of their eligibility for the study. The safety evaluation will be performed based on the first dose of study treatment a patient actually received, regardless of the arm to which he or she was randomized. The safety population will be used for all dosing/exposure, safety, and resource utilization analyses.

Pharmacokinetic analyses will be conducted on all patients who have received at least 1 dose of Abemaciclib and have had samples collected.

Pharmacodynamic and/or tailoring biomarker analyses will be based on the subset of patients from the above populations from whom a valid assay result (according to laboratory guideline) has been obtained.

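### The post-discontinuation therapy line of the resource utilization analysis leaves out randomized patients who never start study drug; it should be summarised in ITT by randomized arm

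*SAP*

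**What the plan says.** SAP 5.2 introduces its list with "The secondary objectives of the study are to compare Abemaciclib plus BSC versus erlotinib plus BSC with respect to", and one entry is "resource utilization (for example, analgesic type, hospitalization, transfusion". Protocol 6.2 has the same objective.

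SAP 6.2.13.1 lists six kinds of resource use. Five (analgesics, transfusions, growth factors, surgery, hospitalizations) are limited to study treatment and short-term follow-up. The sixth, "Post discontinuation radiotherapy and systemic therapy", has no such limit.

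SAP 6.2.2 sets the population: "The safety population will be used for all dosing/exposure, safety, and resource utilization analyses". That population "will include all randomized patients who received any quantity of study treatment, regardless of their eligibility for the study". Protocol 12.2.1 is stricter about what counts as treated: the Safety Population is "defined as all enrolled patients receiving at least 1 dose of any study drug. Patients will be grouped according to treatment received in Cycle 1".

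On follow-up, Protocol 8.1 states that all "randomized patients must be followed during postdiscontinuation regardless of whether study treatment was received". Protocol 7.3.1 requires the scheduled procedures for randomized patients who discontinue, whether or not they took study drug. Footnote g of the study schedule (Protocol Attachment 1) collects survival and subsequent antitumor therapies about every 60 days.

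SAP 6.2.7 (and Protocol 12.2.4.1) separately summarises post-discontinuation therapies overall, by type and by drug name. It names no population.

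**The concern.** What a patient receives after leaving the assigned treatment does not depend on having taken a first dose. A patient who is randomized, never starts and goes straight to another therapy has used the resource that this line is meant to count. The plan follows that patient, records the therapy, and then excludes the patient from the table.

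Two things are at stake. A secondary objective framed as a comparison of the arms is summarised, for this item, on a subset defined by what happened after randomization. And later therapy can influence survival, so a reader of the ITT analysis of OS will want a later-therapy table on the same patients. As written, the resource utilization table does not supply one, and SAP 6.2.7 does not say whether it does.

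**Working it through.** **Reading the sections together**

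1. The objective compares the arms (SAP 5.2, Protocol 6.2).
2. The item has no on-treatment limit (SAP 6.2.13.1, last entry).
3. The population requires treatment (SAP 6.2.2, Protocol 12.2.1), so a randomized patient with no dose is excluded.
4. The same patient is followed, and later therapy is collected (Protocol 7.3.1, Protocol 8.1, Attachment 1 footnote g).

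The exclusion follows from steps 2 and 3. Step 4 shows that it is not forced by a lack of data.

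**Size**

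The plan states no figure on this point. The 304 OS events and about 80% power do not enter.

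Let *u* be the share of an arm never treated, *p* the later-therapy rate in treated patients and *q* the rate in never-treated patients. For one arm:

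- Safety Population rate = *p*
- ITT rate = *p*(1 - *u*) + *qu* = *p* + (*q* - *p*)*u*

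If *p* and *q* are the same in both arms, the Safety Population difference is 0 and the ITT difference (erlotinib minus abemaciclib) is (*q* - *p*)(*u*E - *u*A).

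The documents give none of *u*, *p* or *q*. All values below are assumptions, with *p* = 35%. The differences are in percentage points.

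| Never treated, abemaciclib / erlotinib | *q* = 0% | *q* = 35% | *q* = 60% | *q* = 90% |
|---|---|---|---|---|
| 1% / 1% | 0 | 0 | 0 | 0 |
| 1% / 3% | -0.7 | 0 | +0.5 | +1.1 |
| 2% / 8% | -2.1 | 0 | +1.5 | +3.3 |
| 2% / 12% | -3.5 | 0 | +2.5 | +5.5 |

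Worked example, 1% / 3% with *q* = 90%: abemaciclib 0.35 × 0.99 + 0.90 × 0.01 = 35.55%; erlotinib 0.35 × 0.97 + 0.90 × 0.03 = 36.65%; difference 1.1 points. With *q* = 0 the two rates are 34.65% and 33.95%, a difference of -0.7 points.

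With the planned 270 and 180 patients, 1% and 3% are about 2.7 and 5.4 patients. The 12% row would mean about 21.6 erlotinib patients never starting, and nothing in the documents points to a number that large.

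The zero for equal never-treated shares assumes that *q* - *p* is the same in both arms. If it is not, the shift is (*q*E - *p*E)*u*E - (*q*A - *p*A)*u*A, which need not vanish.

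**The case against.** The strongest reply is that the plan already has a home for this information. SAP 6.2.7 summarises post-discontinuation therapy in its own right and is not labelled safety, exposure or resource utilization. Where the SAP means treated patients only, as in 6.2.8, it says so. On that reading 6.2.7 may well be run on ITT. This stands in part: the mismatch with the OS population is shown only for the line in 6.2.13.1. But 6.2.7 names no population, so nothing ensures that it covers never-treated patients or that the two tables agree.

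Second, the table is descriptive, with no test, alpha or decision rule, and patient disposition (SAP 6.2.5) will report how many were enrolled and treated. That stands, and it keeps the point small.

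Third, one denominator for a whole table is a reasonable preference. It is reasonable for the five items limited to study treatment and short-term follow-up. It does not fit the sixth, which starts where treatment ends or was never begun.

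Fourth, SAP 6.2.2 gives health economics analyses to ITT, which might look like a contradiction because resource utilization sits under health outcomes. That argument is weak. Protocol 10.2.1.2 describes the EQ-5D utilities as input to economic evaluations, so the ITT sentence has its own object, and the sentence that names resource utilization governs.

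A reader might also infer that this line will be compared by drug actually received. SAP 6.2.2 writes that rule for the safety evaluation, and SAP 6.2.14 and Protocol 12.2.1 write the Cycle 1 grouping for safety analyses. Neither document spells it out for resource utilization. The exclusion of never-treated patients does not depend on it.

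**Conclusion.** The point holds and is minor. SAP 6.2.2 excludes randomized patients who never start from the post-discontinuation line of a between-arm secondary objective, although their data are collected. Only a descriptive table is affected. OS, PFS and response are analysed in ITT and do not change.

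The size cannot be fixed from the documents. At 1% against 3% never treated the shift is about -0.7 to +1.1 points under the assumed rates. It grows with the gap in never-treated shares. The sign depends on whether never-treated patients receive more later therapy than treated patients or, for example because they have deteriorated, less.

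A reader might go further: the trial is open-label, erlotinib lost its label and guideline support for these patients in October 2016, so refusals will concentrate in the erlotinib arm and its later therapy will be understated. The documents do not support that. Protocol 5.5 says that "the Sponsor amended the protocol to address the impact on study enrollment completion". That concerns recruitment, not patients declining after randomization, and Protocol section 5 still describes erlotinib as an acceptable control. Differential refusal is possible, but it is not shown.

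**What to change.** - SAP 6.2.2 and 6.2.13.1: summarise post-discontinuation radiotherapy and systemic therapy in the ITT population by randomized arm.
- SAP 6.2.7: state ITT by randomized arm for the post-discontinuation summary, so that the two tables agree.
- Show the number of randomized patients never treated, by arm, beside these tables.
- Keep the Safety Population for the five items limited to study treatment and short-term follow-up.

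The cost is a few sentences in the SAP and a different denominator. The protocol already requires the data from all randomized patients, so no new collection is needed, and neither sample size nor alpha is touched.
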